8.1.2. Temporary Discontinuation from Study Treatment

In certain situations after randomization, the investigator may need to temporarily interrupt study drug. Every effort should be made by the investigator to maintain participants on study drug and to restart study drug after any temporary interruption, as soon as it is safe to do so. Distribution of study medication at the correct dose will be per IWRS instructions.

- If the study drug interruption is ≤ 2 consecutive doses, the drug will be restarted at last administered dose, as per the escalation schedule.
- If the interruption is >2 consecutive doses, the participant will restart study drug at 5 mg (per IWRS instructions) and repeats dose escalation scheme.
- If study drug interruption is due to an AE, the event is to be documented and followed according to the procedures in Section 9.2 of this protocol.
- If the study drug interruption is due to intolerable persistent GI AE (for example, nausea, vomiting, or diarrhea), the participants should be treated as suggested in Section 7.4.2.

Investigators should inform the Sponsor that study drug has been temporarily interrupted. The data related to temporary interruption of study treatment will be documented in source documents and entered on the eCRF.

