5.1.1.2.2. Treatment Period

Randomization (Visit 2)

At Visit 2, eligible participants will perform all required baseline study procedures (including the collection of all baseline laboratory measures and questionnaires) prior to randomization and prior to taking the first dose of study drug. Participants should arrive to the clinic in the fasting state (after a period of approximately 8 hours without eating, drinking [except water], or any significant physical activity and before taking study drug(s)). The mental health questionnaires (Patient Heath Questionnaire-9 [PHQ-9], Columbia-Suicide Severity Rating Scale [C-SSRS], and Self-Harm Form) should be completed after the assessment for AEs.

Participants will receive an initial consultation with a qualified dietitian, according to local standards, to set lifestyle goals for caloric intake and physical activity (Sections 6.3.1 and 6.3.2).

Following randomization, study site personnel will demonstrate use of the autoinjector and observe the study participant inject the first dose of tirzepatide or placebo. The date and time of the first dose of study drug will be recorded on the electronic case report form (eCRF). Beginning at randomization, all participants will receive study drug according to the randomized treatment arm for the duration of the 52-week dose escalation and treatment period.

Treatment Period (End of Visit 2 to Visit 15):

During the treatment period, visits will occur every 4 weeks through 52 weeks. The participant should be fasting for all office visits. Weeks 28, 32, 40 and 48 are telephone visits.

Office visit procedures should be conducted according to the Schedule of Activities (Section 2), and will include

- weight, waist circumference, and vital signs measurements
- review of participant diary information (to include reinforcement and compliance assessments for study drug administration and lifestyle goals)
- administration of questionnaires
- laboratory testing
- drug dispensing, and

• collect AEs and concomitant medications.

Patient-Reported Outcomes (PROs) questionnaires should be administered as early as possible, prior to any other study procedures. All PROs should be completed before any other study procedures if the participant is not adversely affected by the fasting condition or completed after the participant has sufficiently recovered from the preceding visit procedures. Mental Health Questionnaires should be completed after the assessment of AEs.

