Dietitian consultations start at Week 0 and continue at Weeks 4, 8, 12, 24, 36, 44, 52 and early discontinuation (ED). Study drug and injection supplies will be returned per the Schedule of Activities (Section 2) and according to local requirements. New supplies will be dispensed as needed.

Study drug dose escalation is double-blinded and will be managed via the interactive web-response system (IWRS). The starting dose is 2.5 mg QW (or matching placebo) for 4 weeks, then the dose is increased by 2.5 mg (or matching placebo) every 4 weeks (2.5 to 5 to 7.5 to 10 mg) for those randomized to 10 mg, continuing to 12.5 to 15 mg for those randomized to 15 mg. The dose is then maintained for the remainder of the study.

At each of the 4 scheduled telephone visits, procedures will include:

- reinforcement and compliance assessments for study drug administration and lifestyle goals
- listing of concomitant medications
- AE assessment (see Schedule of Activities Section 2), and
- completion of the mental health questionnaires (after the AE assessment).

Participants should be instructed to contact the investigative site for assistance as soon as possible if they experience any difficulties administering their study medication. Participants should also be advised about the appropriate course of action in the event that study drug is not taken at the required time (late/missing doses).

Study participants will be permitted to use concomitant medications that they require during the study, except certain excluded medications (see Section 6.2) that may interfere with the assessment of efficacy and safety characteristics of the study treatments.

Visit 99

Visit 99 is only applicable to participants who discontinue the study treatment prematurely before 52 weeks and decline to complete the remaining study visits but are willing to return for Visit 99 at 52 weeks after randomization. This visit is critical to ensure complete data collection for the primary weight loss endpoint.

Participants should attend this visit in the fasting state. Procedures to be completed are:

- measurement of weight and waist circumference
- listing of concomitant medications
- urine pregnancy test

- assessment of AEs, and
- completion of the mental health questionnaires (after the AE assessment)

For participants unwilling to attend this visit, their refusal to attend should be documented in the participant medical record.

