5.5. Justification for Dose

Tirzepatide doses of 10 mg, and 15 mg QW will be evaluated in this study. These doses and associated escalation schemes were selected based on assessment of safety, efficacy (weight loss), and GI tolerability data, followed by exposure-response modeling of data in patients in Phase 1 and 2 studies.

In a 26-week Phase 2 study (GPGB) of participants with T2DM, tirzepatide reduced body weight by 8.7 kg, and 11.3 kg at dose levels of 10, and 15 mg, respectively, whereas the weight loss

observed in participants on dulaglutide, a selective GLP-1R agonist, used at the dose of 1.5 mg, was 2.7 kg (Frias et al. 2018).

Similar to the GLP-1R agonist class, most of the tirzepatide AEs were dose dependent and GI-related, consisting mainly of nausea, vomiting, and diarrhea. In general, these events were mild or moderate in severity, with few severe episodes, and transient.

Tirzepatide doses of 10 mg, and 15 mg were selected based principally on the following criteria

- each dose provides robust weight loss relative to placebo
- the percent of patients achieving >10% weight loss is higher with 15 mg than 10 mg, and
- safety and tolerability were supported by Phase 2 results and/or PK/PD modeling.

A subsequent Phase 2 study (GPGF) evaluating different titration schemes demonstrated that slower dose escalation and smaller dose increments might improve tolerability. Dosing algorithms starting at a low dose of 2.5 mg accompanied by dose escalation of 2.5 mg increments every 4 weeks should permit time for development of tolerance to GI events and are predicted to minimize GI tolerability concerns. The maximum proposed dose of 15 mg maintains an exposure multiple of 1.6 to 2.4 to the no-observed adverse effect level doses in 6-month monkey and rat toxicology studies.

6. Study Population

Prospective approval of protocol deviations to recruitment and enrollment criteria, also known as protocol waivers or exemptions, are not permitted.

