7.4.2. Management of Participants with Gastrointestinal Symptoms

Participants who experience intolerable GI symptoms (for example: nausea, vomiting, or diarrhea) at any time during the study, should first be counselled on dietary behaviors that may help mitigate nausea and vomiting, (for example, eating smaller meals, splitting 3 daily meals into 4 or more smaller ones, and stopping eating when they feel full). If symptoms persist, the participant should be prescribed, at the investigator's discretion, symptomatic medication (for example, antiemetic or antidiarrheal medication). A temporary interruption of study drug for 1

dose is permitted, provided the participant has taken the last 3 weekly doses. Study treatment should be resumed at the assigned dose immediately, either alone or in combination with symptomatic medication (Appendix 9). Management of study drug after interruptions >1 dose is discussed in Section 8.1.2.

If intolerable GI symptoms (for example, nausea, vomiting, or diarrhea) persist despite the above measures, the investigator should contact Lilly to consider reinitiating study drug at the next lowest maintenance dose in a blinded fashion (for example, 15 mg and 12.5 mg reduced to 10 mg, 10 mg or lower reduced to placebo, the lower dose will be maintained for the rest of the study, with no re-escalation allowed).

If intolerable GI symptoms persist despite symptomatic treatment, temporary drug interruption, and resumption at a lower dose of study drug, the participant should be discontinued from the study drug. Only 1 dose reduction per participant will be permitted during the course of the study. All participants who discontinue study drug should continue to attend scheduled study visits. All dose adjustments will be managed through IWRS.

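### After more than two missed doses, Protocol 8.1.2 restarts a participant last dosed at 2.5 mg on 5 mg, so the longer gap brings the higher dose

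*Protocol*

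**What the plan says.** Protocol 5.1.1.2.2 sets the entry step: "The starting dose is 2.5 mg QW (or matching placebo) for 4 weeks". The dose then rises by 2.5 mg every 4 weeks to 10 mg or 15 mg. Section 5.5 gives the reason for starting low and moving slowly: "dose escalation of 2.5 mg increments every 4 weeks should permit time for development of tolerance to GI events".

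Section 8.1.2 sets the restart dose by the length of the interruption:

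- Two or fewer consecutive doses: "the drug will be restarted at last administered dose, as per the escalation schedule".
- More than two: "If the interruption is >2 consecutive doses, the participant will restart study drug at 5 mg (per IWRS instructions) and repeats dose escalation scheme".

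The second rule does not depend on the dose last taken. A further bullet, beginning "If the study drug interruption is due to intolerable persistent GI AE", sends interruptions with a GI cause to 7.4.2. The 5 mg restart therefore applies most plainly to interruptions with another cause.

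**The concern.** A restart rule should be at least as cautious after a long gap as after a short one. This rule is, for anyone last on 5 mg or more: the restart after a long gap is 5 mg, which equals or lowers the previous dose. The 2.5 mg step is the only one where the dose goes up. A participant there may have had too few injections to build the tolerance that 5.5 relies on, and has then been off drug for at least four weeks. At stake are avoidable GI events, and perhaps avoidable discontinuations, in a small group early in treatment.

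**Working it through.** **Check of the escalation schedule.** With 2.5 mg steps every 4 weeks from week 0, 10 mg starts at week 12 and 15 mg at week 20. That leaves 52 − 12 = 40 weeks and 52 − 20 = 32 weeks at the maintenance dose, which are the figures in Protocol 5.4.

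**Restart dose by last dose, applying 8.1.2 literally.**

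| Last dose | 2 missed | 3 missed | Direction |
|---|---|---|---|
| 2.5 mg | 2.5 mg | 5 mg | up |
| 5 mg | 5 mg | 5 mg | same |
| 7.5 to 15 mg | last dose | 5 mg | down |

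**The 2.5 mg step in detail.** Let k be the number of 2.5 mg injections taken, at weeks 0 to k − 1. After m missed doses the restart falls at week k + m. The calendar dose at week w is 2.5 × (floor(w/4) + 1) mg, up to the assigned dose. Section 8.1.2 can be read in two ways for two missed doses: the dose last administered, or the dose on the calendar schedule.

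| k | 2 missed: week | Last-dose reading | Calendar reading | 3 missed: week | Rule | Calendar dose |
|---|---|---|---|---|---|---|
| 1 | 3 | 2.5 mg | 2.5 mg | 4 | 5 mg | 5 mg |
| 2 | 4 | 2.5 mg | 5 mg | 5 | 5 mg | 5 mg |
| 3 | 5 | 2.5 mg | 5 mg | 6 | 5 mg | 5 mg |
| 4 | 6 | 2.5 mg | 5 mg | 7 | 5 mg | 5 mg |

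For k = 1 the dose rises with the longer gap on both readings. For k = 2 to 4 it does so only on the last-dose reading. For k = 1 to 3 the participant moves to 5 mg with the 2.5 mg step unfinished on either reading. After three or more missed doses the restart is at week 4 or later, when the calendar dose is at least 5 mg, so the rule never runs ahead of the calendar.

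**Length of the gap.** Three missed weekly doses put 4 × 7 = 28 days between injections; two put 3 × 7 = 21 days. The documents give no half-life directly, so a range is inferred:

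- Section 9.4.4 equates Visit 801 with 5 half-lives after the end of treatment. Counting 4 weeks gives 28/5 = 5.6 days.
- Counting from the last dose at week 51 to week 56 gives 35/5 = 7.0 days.
- Appendix 7 equates 5 half-lives plus 90 days with about 4 months. Taking 120 days gives (120 − 90)/5 = 6.0 days.

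The 28-day gap is therefore 4.0 to 5.0 half-lives. Assuming simple exponential decline, the fraction remaining is 2^(−gap/half-life):

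| Half-life | 28-day gap | 21-day gap |
|---|---|---|
| 5.6 days | 3.1% | 7.4% |
| 6.0 days | 3.9% | 8.8% |
| 7.0 days | 6.25% | 12.5% |

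A participant returning after three missed doses thus has about half as much drug left as one returning after two, and receives 5 mg.

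**The case against.** The case for leaving the rule alone has several parts.

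- **The rule for shorter gaps may follow the calendar.** Its closing words in "the drug will be restarted at last administered dose, as per the escalation schedule" allow that reading. If it is right, the contrast by gap length survives only after a single injection. This stands, and the conclusion is limited accordingly.
- **5 mg is on schedule and is not a known hazard.** Section 3.2 reports 5 mg as the maximum tolerated single dose in Phase 1, and weekly 5 mg regimens in patients with type 2 diabetes. Section 8.1.2 also restarts drug only when it is safe and requires the sponsor to be told of interruptions. This stands too. The point concerns GI tolerability and does not show that a 5 mg restart is unsafe.
- **One restart dose is simpler.** True, but IWRS holds the dosing history ("All dose adjustments will be managed through IWRS"), so a cap at the last dose is easy to program.

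A reader might also infer that 8.1.2 overrides the GI dose reduction in 7.4.2: a participant already reduced, who later misses three doses for a non-GI reason, would be re-escalated, or moved from placebo back to active drug. The documents do not support this. Section 7.4.2 says without qualification: "10 mg or lower reduced to placebo, the lower dose will be maintained for the rest of the study, with no re-escalation allowed". The 5 mg rule omits matching placebo for everyone, including the randomized placebo arm, so the omission cannot signify active drug. A participant reduced to 10 mg can satisfy both sections by titrating back to 10 mg and stopping. What is missing is a cross-reference. The Appendix 9 flow chart is not shown in the text available and could not be checked.

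**Conclusion.** The concern holds in a limited form. After more than two missed doses, 8.1.2 takes a participant last on 2.5 mg up to 5 mg, twice the drug-naive starting dose, after at least 28 days without an injection. That this is a higher dose than a shorter gap would bring is certain after one injection; after two to four it holds if the last administered dose is taken literally. With fewer than four injections, the unfinished tolerance step is skipped on either reading.

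The washout comparison rests on an inferred half-life of 5.6 to 7.0 days. The documents give no frequency for such interruptions. Because the restart must follow three consecutive misses very early in treatment, few participants are likely to be affected. Sample size, power and the analyses are untouched. This is a cheap improvement to a dosing rule and is worth making.

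**What to change.** In 8.1.2 and the IWRS specification, state that after more than two consecutive missed doses the restart dose is the lower of 5 mg (or matching placebo) and the last administered dose, followed by the usual escalation.

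**Cost.** Participants restarting from 2.5 mg take one extra 4-week step. This includes anyone who had already completed four 2.5 mg injections; the documents do not say whether tolerance would have lasted. The 15 mg dose is reached at week k + 23 instead of k + 19, that is weeks 24 to 27 instead of 20 to 23. For a week-4 restart with the last dose at week 51, that means 28 weekly doses at 15 mg instead of 32, or 36 at 10 mg instead of 40. For restarts at weeks 5 to 7, the step to 15 mg falls at weeks 25 to 27. The next contacts after week 24 are by telephone ("Weeks 28, 32, 40 and 48 are telephone visits") and the next dispensing visit is week 36, so the week-24 supply may need two strengths.

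**Optional clarification, not a correction.** Add to 8.1.2 that participants reduced under 7.4.2 stay at or below their reduced level, as 7.4.2 already implies, and confirm that IWRS enforces it.

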8.1.3. Discontinuation of Inadvertently Enrolled Participants

If the sponsor or investigator identify a participant who did not meet enrollment criteria and was inadvertently enrolled, the investigator and the Sponsor CRP must agree whether continuing the study treatment is medically appropriate. If the investigator and the sponsor CRP agree it is medically appropriate to continue, the investigator must obtain documented approval from the sponsor CRP to allow the inadvertently enrolled participant to continue in the study with or without treatment with investigational product. Safety follow up is as outlined in Section 2 (Schedule of Activities), Section 9.2 (Adverse Events), and Section 9.4 (Safety) of the protocol.

8.2. Discontinuation from the Study

Participants will be discontinued in the following circumstances:

- enrollment in any other clinical study involving an investigational product or enrollment in any other type of medical research judged not to be scientifically or medically compatible with this study
- participation in the study needs to be stopped for medical, safety, regulatory, or other reasons consistent with applicable laws, regulations, and good clinical practice (GCP)
- investigator decision
 - the investigator decides that the participants should be discontinued from the study
 - o if the participant, for any reason, requires treatment with another therapeutic agent that has been demonstrated to be effective for treatment of the study indication, discontinuation from the study occurs prior to introduction of the new agent
- subject decision
 - o the participant requests to be withdrawn from the study

To minimize the amount of missing data and to enable assessment of study objectives as planned in the study protocol, every attempt will be made to keep participants in the study irrespective of the following:

[figure not shown]
- adherence to or discontinuation from study drug
- adherence to visit schedule
- missing assessments
- study drug discontinuation due to AE
- development of comorbidities
- development of adverse clinical outcomes

The circumstances listed above are *not* valid reasons for discontinuation from the study.

Participants who agree to provide information relevant to any trial endpoint at the end of the study are not considered to have discontinued from the study.

Participants discontinuing from the study prematurely for any reason should complete adverse event and other safety follow-up per Section 2 (Schedule of Activities), Section 9.2 (Adverse Events), and Section 9.4 (Safety) of this protocol.

8.2.1. Participant disposition and timing of safety follow-up for the primary endpoint (52 weeks)

Abbreviations: ED=early discontinuation; Pt= participant; wks=weeks

Figure GPIA.2. Illustration of participant disposition and safety follow-up for Clinical Protocol I8F-MC-GPIA.

8.3. Lost to Follow-Up

A participant will be considered lost to follow-up if he or she repeatedly fails to return for scheduled visits and is unable to be contacted by the study site. Site personnel are expected to make diligent attempts to contact participants who fail to return for a scheduled visit or were otherwise unable to be followed up by the site.

Site personnel, or an independent third party, will attempt to collect the vital status of the participant within legal and ethical boundaries for all participants randomized, including those who did not get investigational product. Public sources may be searched for vital status information. If vital status is determined, this will be documented, and the participant will not be considered lost to follow-up.

Eli Lilly and Company personnel will not be involved in any attempts to collect vital status information.

Discontinuation of specific sites or of the study as a whole are handled as part of Appendix 4.

9. Study Assessments and Procedures

Appendix 2 lists the laboratory tests that will be performed for this study. Repeat or unscheduled samples may be taken for safety reasons or for technical issues with the samples.

Unless otherwise stated in the subsections below, all samples collected for specified laboratory tests will be destroyed within 60 days of receipt of confirmed test results. Certain samples may be retained for a longer period, if necessary, to comply with applicable laws, regulations, or laboratory certification standards.

9.1. Efficacy Assessments

9.1.1. Primary Efficacy Assessments

The primary efficacy measurement in this study is the body weight. Body weight measurements will be collected at specific clinic visits as summarized in the Schedule of Activities (Section 2). Methods for measuring body weight are described in Appendix 8.

9.1.2. Secondary Efficacy Assessments

The following secondary efficacy measures will be collected at the times shown in the Schedule of Activities (Section 2) and analyzed in a manner controlled for type I error:

- Body weight (measuring method is described in Appendix 8)
- Waist circumference (measuring method is described in Appendix 8)
- HbA1c (%) (measured through central lab)
- Fasting glucose (mmol/L) (measured through central lab)
- Blood pressure (measuring method is described in Appendix 8)
- Fasting lipids (mmol/L) (measured through central lab)
- Fasting insulin (measured through central lab)

9.1.3. Patient-Reported Outcomes Assessments

The self reported questionnaires will be administered according to the Schedule of Activities (Section 2). At these visits, the questionnaires should be completed before the participant has discussed their medical condition or progress in the study with the investigator and/or site staff if the participant is not adversely affected by their fasting condition.

9.1.3.1. Short Form 36 version 2, acute, 1 week recall version

The SF 36v2 acute, 1 week recall version is a 36 item generic, patient-administered measure designed to assess the following 8 domains of health-related quality of life (HRQoL) "in the past week," except for the Physical Functioning domain, which assesses an individual's physical function in terms of how their health limits them "now" (i.e., currently):

- Physical Functioning
- Role Physical
- Bodily Pain

- General Health
- Vitality
- Social Functioning
- Role Emotional, and
- Mental Health

Information from these 8 domains are further aggregated into 2 health component summary scores: Physical Component Summary and Mental Component Summary. Items are answered on Likert scales of varying lengths. Scoring of each domain and both summary scores are norm based and presented in the form of T scores, with a mean of 50 and standard deviation of 10; higher scores indicate better levels of function and/or better health (Maruish 2011).

